8.6.1.3 Adverse events by severity

The number of subjects and incidence rate should be calculated for adverse event and adverse drug reaction by severity for the overall and for individual events classified by SOC and PT.

The tabulation method by severity (severe, moderate, mild) is as follows.

When adverse events of different severity occur in the same subject, the most severe adverse event should be counted as one subject.

When multiple adverse events of the same severity occur in the same subject, the same severity should be counted as 1 subject.

When the same subject experienced the same adverse event multiple times, the most severe adverse event should be counted as 1 subject.

8.6.1.4 Adverse events by the time of onset

The number and incidence rate of subjects with adverse events and adverse drug reactions should be calculated for adverse event and adverse drug reaction by time of onset (every 12 weeks) for the overall and for individual events classified by SOC and PT. For the calculation of the incidence rate, the number of subjects at each evaluation time point is used as the denominator. (Tabulation unit: from the first day of the treatment period [Day 1] to Day 84, Days 85–168, Days 169–252, Days 253–364, and after Day 365)

However, if the same adverse event occurs in different categories in the same subject, it is counted as 1 subject in each category.

8.6.1.5 Adverse events by dose immediately before onset

The number and incidence rate of adverse events and adverse drug reactions in overall and individual events classified by SOC and PT per total exposure period should be calculated for each treatment group by dose immediately before onset*. The total exposure period is defined as the total number of months (months) that each dose was administered during the study period.

The following formula is used to calculate the number of months of exposure. Number of months of exposure = number of days of exposure/30.4375

*The tabulation unit for each event by dose immediately before onset should be as follows:

MT-6548 group: daily dose (tabulation unit: 0 mg, 150 mg, 300 mg, 450 mg, 600 mg)

Darbepoetin group: weekly dosage (tabulation unit: 0 µg, >0 µg to ≤30 µg, >30 µg to ≤60 µg, >60 µg to ≤90 µg, >90 µg to ≤120 µg, >120 µg)

8.6.1.6 Adverse events by cumulative dosage

The number of subjects and incidence rate should be calculated for adverse event and adverse drug reaction by cumulative dosage before onset for the overall and for individual events classified by SOC and PT. The cumulative dosage will be divided into 4 categories at quartiles (0 to 1/4 of the maximum cumulative dosage, 1/4 to 2/4 of the maximum cumulative dosage, 2/4 to 3/4 of the maximum cumulative dosage, and ≥3/4 of the maximum cumulative dosage). In addition, the average number of exposure days per person should be calculated for each category. (Average number of exposure days: in the case of “0–x/4 of the Maximum Cumulative dosage”, the number of days until the subject concerned reaches x/4 of the maximum cumulative dosage should be calculated for each subject. In the case of ≥3/4 of the maximum cumulative dosage, the number of days to final administration for each subject and the mean should be calculated.)

The tabulation unit by cumulative dosage is as follows: However, if the same adverse event occurs in different categories in the same subject, it is counted as 1 subject in each category.

4 categories (cumulative unit: ≥0 to <1/4* maximum cumulative dosage, ≥1/4 to < 2/4* maximum cumulative dosage, ≥2/4 to <3/4* maximum cumulative dosage, ≥3/4* maximum cumulative dosage).

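### Adverse events by cumulative dosage (SAP 8.6.1.6): the maximum is undefined and time in band is left out of the incidence, which under a group maximum tends to fall at constant risk

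*SAP*

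**What the plan says.** Final SAP 8.6.1.6 asks for the following: "The number of subjects and incidence rate should be calculated for adverse event and adverse drug reaction by cumulative dosage before onset". On the bands it says "The cumulative dosage will be divided into 4 categories at quartiles", and explains these in brackets as "0 to 1/4 of the maximum cumulative dosage, 1/4 to 2/4 of the maximum cumulative dosage", continuing in the same way up to three quarters and above. These are equal slices of a maximum. They are not quartiles of a distribution. The text does not say whose maximum is meant.

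The counting rule is "if the same adverse event occurs in different categories in the same subject, it is counted as 1 subject in each category". No denominator is named for the incidence.

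Exposure time does appear: "In addition, the average number of exposure days per person should be calculated for each category". For the bands below the top one it is defined as "the number of days until the subject concerned reaches x/4 of the maximum cumulative dosage should be calculated for each subject"; for the top band it runs to the last dose. Both are counted from the start of treatment. Nothing is said about subjects who never reach a threshold.

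Phase 1 SAP 8.6.1.6 uses the same bands and the same exposure days.

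The neighbouring sections of the Final SAP do name a denominator. In 8.6.1.4: "For the calculation of the incidence rate, the number of subjects at each evaluation time point is used as the denominator". In 8.6.1.5 the rate is "per total exposure period should be calculated for each treatment group by dose immediately before onset", with exposure in months of 30.4375 days.

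**The concern.** Every subject starts at zero cumulative dose and so spends time in the lowest band. With a threshold common to the group, subjects on low or unchanged doses stay in the lower bands all year, and only those on higher doses reach the top, late and often briefly. The chance of an event in a band then depends largely on the time spent there. A count of subjects with an event, divided by all subjects or by those entering the band, mixes risk with time at risk.

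This is the one table in the plan that sets adverse events against accumulated exposure, and long-term safety is a study objective. If the percentages fall across bands for a structural reason, a reader may take that as reassurance about accumulating dose. Because the maximum is undefined, two programmers could also produce quite different tables from the same text.

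**Working it through.** The section states no figure, so there is none to reproduce. The check has three steps.

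**1. Days in each band from the dosing rules (group maximum).** Inputs from protocol 8.3.1 and 8.4: start at 300 mg daily, range 150 to 600 mg, increases of one 150 mg tablet at least 4 weeks apart, 364 dosing days. The steepest path gives

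300 × 28 + 450 × 28 + 600 × 308 = 205,800 mg; one quarter = 51,450 mg.

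Assigning each day to a band by the dose accumulated before it:

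| Path (changes from day 29) | Total, mg | Share of maximum | Days in bands 1 / 2 / 3 / 4 |
|---|---|---|---|
| Reduced to 150 mg | 58,800 | 29% | 315 / 49 / 0 / 0 |
| 300 mg throughout | 109,200 | 53% | 172 / 171 / 21 / 0 |
| Raised to 450 mg | 159,600 | 78% | 124 / 114 / 115 / 11 |
| Raised to 450, then 600 mg | 205,800 | 100% | 107 / 86 / 86 / 85 |

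The top band starts at 0.75 × 205,800 = 154,350 mg, an average of 154,350 / 364 = 424 mg a day. A subject at 300 mg throughout would reach it only if the group maximum were at most 109,200 / 0.75 = 145,600 mg, meaning that nobody averaged more than 145,600 / 364 = 400 mg a day.

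The 24-week analysis behaves alike. Over 168 days the steepest path is 300 × 28 + 450 × 28 + 600 × 112 = 88,200 mg, one quarter is 22,050 mg, and 300 mg throughout gives 74 / 73 / 21 / 0 days.

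**2. What this does to the incidence.** With a constant hazard of 0.05 per month (assumed), the chance of at least one event in a band is 1 − exp(−0.05 × days / 30.4375). At 300 mg throughout this is 24.6%, 24.5%, 3.4% and 0%, although the risk never changes.

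For a whole arm, 400 trials of 150 MT-6548 subjects were simulated. Assumptions that are not in the documents: the same baseline hazard; 15% dropout spread evenly over time; the four paths above in proportions 20 / 40 / 25 / 15%. For the group maximum, the bands are quarters of the largest cumulative dose in each simulated trial.

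| Maximum and true risk by band | Measure | Band 1 | Band 2 | Band 3 | Band 4 |
|---|---|---|---|---|---|
| Group, constant | % of all subjects | 23.8 | 15.9 | 6.7 | 2.1 |
| | % of those entering band | 23.8 | 17.1 | 9.4 | 6.2 |
| | events per 100 person-months | 4.95 | 4.96 | 4.97 | 5.16 |
| Group, × 1, 1.33, 1.67, 2 | % of all subjects | 23.9 | 20.5 | 10.8 | 4.0 |
| | % of those entering band | 23.9 | 22.2 | 15.3 | 11.7 |
| | events per 100 person-months | 4.98 | 6.65 | 8.46 | 10.27 |
| Group, × 1, 2, 3, 4 | % of all subjects | 24.1 | 28.6 | 17.2 | 7.0 |
| | % of those entering band | 24.1 | 30.9 | 24.3 | 20.5 |
| Own, constant | % of all subjects | 12.8 | 13.1 | 12.7 | 13.0 |
| Own, × 1, 1.33, 1.67, 2 | % of all subjects | 12.9 | 16.9 | 20.5 | 23.9 |

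Other mixes of the four paths under the group maximum, as % of all subjects:
- Lower doses (30 / 45 / 20 / 5%), constant risk: 26.4, 15.4, 4.9, 0.9. Doubling risk: 26.2, 20.0, 7.9, 1.7.
- Higher doses (5 / 25 / 30 / 40%), constant risk: 19.4, 15.9, 9.9, 5.0. Doubling risk: 19.5, 20.0, 16.0, 9.4.

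**3. Whether the planned exposure days repair it.** On the 600 mg path they are 107, 107 + 86 = 193, 193 + 86 = 279, and 364 for the top band. The days actually spent in the bands are 107, 86, 86 and 85. At 300 mg throughout the planned days are 172 and 343, with no value for three quarters because that threshold is never reached. Dividing by the printed days would therefore not give a rate for the band.

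**The case against.** **The maximum may be each subject's own.** The SAP does not exclude this, and having no rule for subjects who miss a threshold fits it, since everyone would then reach every band. Under that reading the simulation gives about 84 days in every band, a flat incidence at constant risk and a visible rise when risk doubles. This stands: the artefact is conditional. The group reading is still more natural, because the section asks when a subject reaches a fraction of the maximum, and a subject's own total is already what 4.10 calls the cumulative dosage. The own reading also has a cost: one band would mix very different amounts in mg, and an event that ends treatment would usually land in that subject's top band. The simulation did not model the latter.

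**Exposure is not ignored.** A reader might infer that it is. The section does require mean exposure days for each category. The narrower point is that they are outside the denominator and are not days within the band.

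**The incidence need not fall.** A reader might infer a fall by construction. When risk quadruples, or doubles with more subjects on high doses, the second band exceeds the first. What stayed constant in every group-maximum case run is that the last band was below the first.

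**Other tables give cover.** A reader might infer that a rising risk would go unseen in the whole safety output. The documents do not support that: 8.6.1.4 tabulates onset by 12-week period and 8.6.1.5 gives exposure-adjusted rates by dose before onset. Neither addresses cumulative dosage, so the cover is partial. The table at issue has no test or decision rule attached.

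**Conclusion.** The point holds in conditional form. The label and the definition of the bands disagree, the maximum is not specified, and the incidence has no stated denominator and no adjustment for exposure. If the maximum is common to the group, the protocol's own dosing arithmetic puts most time at risk in the lower bands. Count-based incidence then tends to fall at constant risk and can mask a moderate rise such as a doubling, whether the denominator is all subjects or those entering the band.

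The days per band for each path follow from the protocol. The simulated percentages do not: they rest on an assumed hazard, dropout and dose mix, and only their direction should be relied on. At constant risk that direction was the same in all three mixes tried. The 52-week figures are for MT-6548; nothing was calculated for darbepoetin. Because this is one descriptive safety table, the point is a worthwhile and inexpensive improvement. It is not a threat to the trial's conclusions.

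**What to change.** In 8.6.1.6 of both SAPs:

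1. State that the maximum is the largest cumulative dosage observed in the treatment group.
2. Replace 'quartiles' with 'quarters of the maximum cumulative dosage'.
3. For each band, report events (or subjects with a first event) per exposure-month accrued within that band, using the month of 30.4375 days from Final SAP 8.6.1.5. If first events are used, stop counting a subject's time in the band at the event. Show the subject counts alongside.
4. Define the mean exposure days as days within the band among subjects who enter it, so that subjects who miss a threshold are handled explicitly.

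The cost is a few lines of SAP text and modest programming, since the days to each threshold are already to be derived. Rates replace simple percentages, which some readers find less direct. Top-band rates will be imprecise: in the doubling scenario that band held about 2,001 person-days per trial, or 2,001 / 30.4375 ≈ 66 months, so about 66 × 0.10 ≈ 7 events. Because dose is titrated to Hb, cumulative dosage is tied to response and time on treatment. The rates therefore remain descriptive and do not isolate a causal effect of cumulative dose.

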8.6.1.7 Adverse events before and after drug interruption

The number of subjects and incidence rate should be calculated for adverse event and adverse drug reaction by before and after drug interruption for the overall and for individual events classified by SOC and PT. It should be classified to 2 categories: 4 weeks before drug interruption and 4 weeks after

drug interruption (4 weeks after the start of drug interruption). If a subject had multiple drug interruptions and the adverse event occurred within 4 weeks after the drug interruption and within 4 weeks before the drug interruption, the subject should be counted as 1 subject for both periods.

Drug interruption period is defined as the period when “Yes” was selected in the question of “Did you choose the dosage according to the dosage adjustment algorithm?” and “0 mg” for the MT-6548 group or “0 µg” for the darbepoetin group was selected in the question of “Whether the dose was changed” in the “Administration status” of the case report form. If “No” is selected in the question of “Did you choose dosage according to dosage adjustment algorithm?”, the subject should not be included in the calculation.

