8.3 Dosage and administration

8.3.1 MT-6548 Tablet

- (1) Initial dosage levels
 - 1) Initial dosage for correction cohort
Single daily dose of 300 mg (2 tablets)
 - 2) Initial dosage for conversion cohort
Single daily dose of 300 mg (2 tablets)
- (2) Maintenance dosage and dosage adjustments
Maintenance dosage is 150 to 600 mg once daily and adjusted according to the dosage adjustment guideline below.

MT-6548 Tablet dosage adjustment guidelines

Investigators/subinvestigators will monitor Hb levels throughout the treatment period, and determine whether to adjust study drug dosage or discontinue administration as required. In principle dosage adjustments are to be performed at scheduled study visits, but they may also be performed at unscheduled visits if considered necessary, for example if Hb level variation gives concern for excessive increases or decreases.

Hb levels will be measured on scheduled study visit with the HemoCue® Hb201 DM analyzer; in principle these measurements will be used for determinations regarding dosage adjustments. Hb measurements used for dosage adjustment determinations will be recorded in the subject's case report form (CRF). Measurement results from the HemoCue® Hb201 DM will be used solely for determination of study drug dosage adjustments, and will not be used for efficacy or safety analysis.

The dosage adjustment algorithm below will be followed in order to maintain Hb levels of 11.0–13.0 g/dL during the study. Dosage adjustment steps are defined in the chart below.

MT-6548 Tablet dosage adjustment chart

Step	No. of tablets	Dosage
1	1	150 mg
2	2	300 mg
3	3	450 mg
4	4	600 mg

*It is permitted for dosage adjustments not to comply with the dosage adjustment algorithm for safety reasons depending on factors such as clinical status (e.g., AEs, volume depletion, or volume overload), Hb elevation rate, decrease rate, or fluctuations. In such cases, clinical status will be recorded in CRFs. All dosage increases of MT-6548 will be in increments of 1 tablet at a time.

If a dosage increase or reduction according to the dosage adjustment algorithm is impossible because the maximum or minimum dosage on the dosage adjustment chart is already being administered, it is permitted to not alter the dosage at that point. However, in this case it will be confirmed whether withdrawal criteria are met, and treatment discontinued if so.

Dosage adjustment algorithm for MT-6548 Tablet

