12.3 The criteria of the temporary discontinuation of study drugs

Subjects will temporary discontinue the study drug if either of the following criteria is met:

- (1) Based on the dosage adjustment guideline. (Refer to “8.3 Dosage and administration” for detail)
- (2) ALT or AST > 3x ULN without total bilirubin > 2x ULN during the study.

Rationale

- (1) (2) Set out of safety considerations.

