4.5 Number of days of drug interruptions

The number of days of drug interruptions does not include subject's forgetting to take the drug and is defined by the following formula. Number of days of drug interruptions (days) = Date of resumption of study drug administration – Start date of study drug interruption.

If there are multiple interruptions, the sum of them should be used.

Resumption date of study drug: After the entry of "Daily Dose" = 0 mg or 0 μg in the CRF, the first dose should be taken when a value of >0 mg is entered for the first time, or when a value of >0 μg is entered for the first time. If the drug interruption continues until Week 52 of the treatment period, days should be calculated based on the visit date after Week 52 of the treatment period as the resumption date. Specifically, if the treatment is completed or discontinued while the drug is interrupted, the day before the day of blood sampling at Week Treatment period 52 for hematology tests or the day before the day of treatment discontinuation should be used.

First day of study drug interruption: First day of administration when "Daily Dose" = 0 mg is first entered in the CRF or first day of administration when 0 μg is entered.

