8.6.11 Hb level after dose reduction or interruption of the study drug

Descriptive statistics of Hb values at dose reduction/drug interruption and after dose reduction/drug interruption of the study drug should be calculated for each treatment group. In addition, the change of Hb after dose reduction/drug interruption of the study drug should be determined, and descriptive statistics should be calculated for each treatment group. For the Hb value after dose reduction/drug interruption of the study drug, the data of the day closest to 4 weeks (28 days) after the Hb measurement day at dose reduction/drug interruption should be adopted. If no study drug data at the time of dose reduction/drug interruption are available, subjects should be excluded from the Hb value analysis. In addition, the interval (days) from the Hb measurement in dose reduction/drug interruption of the study drug to the Hb measurement after dose reduction/drug interruption should be calculated, and the descriptive statistics should be provided in each treatment group. A similar analysis should be performed for each patient cohort.

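### The table of adverse events before and after drug interruption covers only holds made under the dosing algorithm and drops the subject on a No answer, so AE- and liver-driven holds probably leave it

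*SAP*

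**What the plan says.** Section 8.6.1.7 has the same definition in the final SAP and the Phase 1 SAP. It counts subjects with AEs and adverse drug reactions, overall and by SOC and PT, in two windows: 4 weeks before an interruption and 4 weeks from its start. It allows for several interruptions per subject. The definition is: "Drug interruption period is defined as the period when “Yes” was selected in the question of “Did you choose the dosage according to", which goes on to name the dosing algorithm and a CRF dose of 0 mg or 0 µg. On a No answer, "the subject should not be included in the calculation".

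Final SAP 4.5 treats interruptions more broadly when it counts days. An interruption starts when "0 mg is first entered in the CRF" (or 0 µg for darbepoetin) and runs to resumption. Only forgotten doses are left out, and the algorithm question plays no part.

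On why drug is held, the algorithms in Protocol 8.3.1 and 8.3.2 stop drug at Hb above 13.5 g/dL, or above 13.0 and up to 13.5 g/dL with a sudden rise. The same sections add: "It is permitted for dosage adjustments not to comply with the dosage adjustment algorithm for safety reasons depending on factors such as clinical status", with AEs as the first example. Protocol 12.3 gives two criteria for a temporary stop: the dosage adjustment guideline and, separately, "ALT or AST > 3x ULN without total bilirubin > 2x ULN during the study".

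Final SAP 8.6.12 applies the same Yes condition, plus a rescue exclusion, to Hb after an interruption. Phase 1 SAP 8.6.11 asks for "Descriptive statistics of Hb values at dose reduction/drug interruption and after dose reduction/drug interruption of the study drug" with neither condition.

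**The concern.** The title of 8.6.1.7 covers drug interruptions in general, but its definition selects on how the dosing decision was made. If a hold made because of an AE or a liver value is recorded as not following the algorithm, the holds most closely tied to an AE are the ones left out. Subjects would then be excluded from an AE table on a decision related to the outcome being tabulated.

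This matters for two reasons. Protocol 9.2.4.2 asks investigators to consider whether an event goes away after stopping when they judge causality, and 8.6.1.7 is the only planned table that sets AEs before a hold beside AEs after it. Also, the No rule is worded by subject and is not tied to a zero-dose entry. Two programmers could reasonably produce different tables from it.

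**Working it through.** No formula in the plan applies and there is no stated figure to reproduce. The check is a comparison of definitions by type of hold.

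| Type of zero-dose period | SAP 4.5 day count | SAP 8.6.1.7 AE table |
|---|---|---|
| Hb hold under the algorithm | in | in (Yes) |
| AE-driven hold outside the algorithm | in | probably out (No) |
| ALT/AST hold under Protocol 12.3(2) | in | probably out (No) |
| Forgotten dose | out | out |

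1. **Why the second and third rows are probably No.** Every hold rule inside the algorithm is an Hb rule. Protocol 8.3 describes safety-driven dose decisions as not complying with the algorithm, and 12.3 lists the liver criterion apart from the guideline. The remaining step, how sites answered the CRF question, is inferred. Where an Hb trigger and an AE coincide, the answer could be Yes.

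2. **Why these holds are linked to the outcome.** Under Protocol 9.2.4.2, a laboratory abnormality that leads to a drug holiday is treated as clinically problematic, and so as an AE. A liver-driven hold therefore comes with an AE by the protocol's own rule.

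3. **What a literal reading of the No sentence does.** Take a subject with one Hb hold answered Yes and one AE hold answered No. Per interruption, the Hb hold stays and the AE hold goes. Per subject, both go. Because the sentence does not mention a zero dose, a single off-algorithm dose change that was not a hold would have the same effect.

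4. **What other tables give.** Final SAP 8.2.2 counts interruptions by reason, with a hepatic category. Sections 8.6.1.1 and 8.6.1.2 count AEs that led to a reduction or hold. Section 8.6.3 counts liver thresholds. Section 8.6.1.5 gives AEs by last dose before onset, including a 0 mg/0 µg category over exposure time. None requires a Yes answer, and none compares the weeks before a given hold with the weeks after it.

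5. **Why no size can be given.** The documents contain no count of interruptions by reason and no AE rate around them. Assumed values would not help. Let a share q of holds be AE-driven, each with an AE beforehand by definition, and let b be the background AE probability in 4 weeks. The pooled rate before the hold is q + (1 − q)b, which exceeds b by q(1 − b). That excess is positive for any q above 0 and b below 1, whatever the drug does, so a figure built this way only returns its own assumption.

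**The case against.** The strongest defence is that the restriction is good design. A hold triggered by Hb is not triggered by the AE being counted, so before and after can be compared without built-in selection. Pooling AE-driven holds would produce a fall after stopping even for an inert drug, as step 5 shows. This stands, and it is a reason to keep the algorithm holds as their own table. It does not justify a title that covers all interruptions, a subject-level exclusion, or leaving the other holds without any before-and-after display.

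Second, a reader might infer that SAP 4.5 and 8.6.1.7 contradict each other. They do not. Section 4.5 feeds the administration-day and compliance formulas in 4.7 and 4.8, where the reason for a hold is irrelevant. A table may carry its own definition.

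Third, the events appear in the other tables listed above, so they do not disappear from the safety report. This also stands, and it confines the point to one table.

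Fourth, the subject-level loss rests on one clause in a translated document. The same section speaks of periods and of several interruptions per subject, so a per-interruption reading is available. What is established is an ambiguity that the SAP should settle.

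**Conclusion.** The point holds in a limited form. As written, 8.6.1.7 in both SAPs confines the table to holds answered Yes. It probably omits AE- and liver-driven holds and, on a literal reading, discards valid algorithm interruptions from any subject with a No. The first consequence assumes that such holds were answered No; the second assumes the subject-level reading.

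The size is unknown. A reader might infer that AE rates before interruption are understated, or that a fall in AEs after stopping could not be seen at all. The documents do not support either. For the interruptions the section defines, the rate before the hold is what it is, and a fall around algorithm holds remains visible. What cannot be seen is the pattern around the holds that are excluded.

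The algorithm and rescue restrictions in final SAP 8.6.12 suit its subject, Hb after a hold. Its table and that of Phase 1 SAP 8.6.11 cover differently selected subjects, and the SAP should say so. The table in 8.6.1.7 is descriptive and carries no hypothesis test. The primary efficacy analysis is unaffected. The change is worth making because it is cheap, not because a conclusion depends on it.

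**What to change.** In 8.6.1.7 of both SAPs:

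- apply the No exclusion to the interruption, not the subject;
- keep the Yes interruptions as the present table and title it as algorithm-based interruptions;
- add a separate block, not pooled with the first, for non-algorithm interruptions split into AE, hepatic criterion and other;
- add a footnote that a fall after AE-triggered holds is partly expected from selection.

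In final SAP 8.6.12, keep the algorithm and rescue restrictions but apply them per interruption. State that Phase 1 SAP 8.6.11 had no such restriction, so the two tables are not directly comparable.

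No new data are needed. Protocol 9.2.2.1 and 9.2.2.2 already record reasons for drug holidays in both arms, and final SAP 8.2.2 already identifies hepatic interruptions from coded comments. The cost is SAP wording and one extra row block. The change concerns tabulation only and touches no dosing or stopping rule.
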